WEXNER MEDICAL CENTER

COVER LETTER

Document date: 01/09/2017

Comparison of Blood Product Use and Bleeding Events During and After Endoscopic or Neurosurgical Procedures in Patients with Cirrhosis and Coagulopathy: Rotational Thromboelastometry Versus Conventional Therapy

NCT02457403

WEXNER MEDICAL CENTER

SCARLET: A Prospective, Randomized Clinical Trial Comparing Blood Product Use and Bleeding Events During and After Endoscopic or Neurosurgical Procedures in Patients with Cirrhosis and Coagulopathy: Rotational Thromboelastrography (ROTEM) versus Conventional Therapy.

Principal Investigator: A. [name]

I. Objective

This is a prospective, single center, randomized clinical trial in patients with cirrhosis and associated coagulopathy undergoing endoscopic or neurosurgical intervention, investigating outcomes including blood product use and bleeding events in patients who receive Rotational Thromboelastography (ROTEM) versus conventional, laboratory-based coagulation methods.

II. Background

The liver produces most of the proteins involved in coagulation and those that regulate it [1]. In liver disease, production of procoagulants and anticoagulants is impaired, fibrinolysis is altered, and there is a reduction in platelet number and function [2]. These various abnormalities of the coagulation system in liver disease can be characterized by measuring individual components. However, this does not give a global account of blood coagulation and the risk of spontaneous or iatrogenic bleeding. Standard coagulation tests such as prothrombin time (PT), activated partial thromboplastin time (aPTT), international normalized ratio (INR), fibrinogen, and platelet count are limited in their inability to assess clot strength and the functionality of fibrinogen or hyperfibrinolysis that may be present, especially in the presence of liver disease. There is also a lack of real time monitoring. This is one of the greatest benefits of using ROTEM point of care testing, as changes in coagulation can be evaluated throughout a procedure. ROTEM monitors viscoelastic properties of clot formation and degradation, allowing for a comprehensive view of the entire coagulation process. The viscoelastic reaction in the clot formation processes are assessed by ROTEM as follows: clotting time measures the start of clot formation, clot formation time measures the initial rate of fibrin polymerization and clot formation dynamics and kinetics, A10 measures the amplitude at 10 minutes after the end of clotting time, maximum clot firmness measures the maximal viscoelastic strength of the clot, and maximum lysis measures the percentage in the decrease of amplitude in relation to the maximum clot firmness. A maximum lysis value of greater than 15% is used to diagnosis hyperfibrinolysis or premature clot lysis.

Several studies utilizing ROTEM have shown that maximum clot firmness and fibrinogen levels are reliable predictors of perioperative bleeding complications and need for massive transfusions of blood products [3]. In patients undergoing liver transplantation, use of ROTEM guided hemostatic therapy correctly predicted hypofibrinogenemia, thrombocytopenia, and decreased clot firmness [4]. Furthermore, researchers suggest that while PT and INR are used as a prognostic indicator and to guide blood product management, that these tests are poor predictors of bleeding risk in liver disease [5]. This is an important realization, which challenges the current practice of correcting an abnormal INR with fresh frozen plasma prior to invasive procedures, even though INR cannot accurately predict bleeding risk, as it measures only one of the many components of coagulation and clot stability. Used in other scenarios where coagulopathy is encountered, studies have revealed the utility of ROTEM use in liver transplantation, significant hemorrhage, cardiac surgery, and detecting coagulation disorders in trauma [6].

WEXNER MEDICAL CENTER

Application of ROTEM hemostatic therapy and algorithm-guided blood products resuscitation before and during endoscopies may lead to more judicious use of blood products for cirrhotic patients with coagulopathy, as point of care testing will reveal information on the coagulation status of the patient to guide transfusions. In cardiac surgery patients who also had coagulopathy, point of care ROTEM testing resulted in lower cumulative blood product usage (including packed red blood cells, pooled platelets, and fresh frozen plasma), as well as lower post-operative mechanical ventilation time, length of intensive care unit stay, and six month mortality [7]. Cirrhosis-related coagulopathies represent an even more significant derangement in natural clotting and anticoagulation factors, and ROTEM may provide a more holistic approach to understanding where a particular patient lies on the spectrum from a high bleeding risk to a high clotting risk.

III. Procedures

A. Research Design

The objective of this study is to investigate blood product use, bleeding events, hospital length of stay, and health care costs in hospitalized patients with cirrhosis and coagulopathy undergoing endoscopy or neurosurgical procedures utilizing ROTEM compared to conventional therapy. Data will be extracted from charts in the electronic medical record (IHIS). Data from charts will be used to construct a secure database of information on risk factors and pre-procedure testing (see Appendix 1). This database will allow analysis of clinical outcomes in patients with cirrhosis undergoing an endoscopic or surgical procedure.

In this prospective study, patients will be randomized into one of two groups:

-Study Group: those who receive blood product transfusions based on ROTEM-guided protocol (Appendix 2). -Control Group: those who receive blood product transfusions based on conventional, laboratory-guided parameters (Appendix 3).

The randomization list will be computer-generated using a balanced allocation ratio of 1:1. The endoscopist or surgeon performing the procedure will be blinded to the patient's group.

B. Hypothesis

The ROTEM- guided transfusion protocol will significantly decrease blood product usage without any increase in procedural bleeding complications versus the conventional, laboratory-based transfusion protocol in patients with cirrhosis undergoing endoscopy and neurosurgical procedures.

C. Objectives

Primary Objective

To compare the total amount of pre-procedure blood products transfused between the ROTEM-guided transfusion protocol and conventional, laboratory-based transfusion protocol in patients undergoing endoscopy and neurosurgical procedures. Endoscopy procedures include esophagogastroduodenoscopy, colonoscopy, flexible sigmoidoscopy, endoscopic retrograde cholangiopancreatography, and endoscopic ultrasound. Neurosurgical procedures may include bedside procedures (e.g. placement of an external ventricular drain or placement of an intracranial pressure monitor), or any neurosurgical cranial or spinal procedure that occurs in the operating room

WEXNER MEDICAL CENTER

during the patient's admission (e.g. craniotomy for evacuation of hematoma or a spinal fusion procedure to address spinal instability).

Secondary Objectives

- 1. Compare the rate of bleeding events between ROTEM vs. conventional therapy:
 - Clinically significant peri-procedure blood loss as documented by the endoscopist or surgeon performing the procedure
 - Major bleeding during the 24 hours post-procedure, defined as a decrease in hemoglobin of ≥ 2 g/dL or requiring a transfusion of ≥ 2 units of packed red blood cells.
- 2. Compare length of stay between ROTEM vs. conventional therapy
- 3. Compare hospitalization costs between ROTEM vs. conventional therapy

D. Sample

202 patients with cirrhosis and coagulopathy who are undergoing an endoscopic or neurosurgical procedure, at The Ohio State University Wexner Medical Center will be enrolled into the study using the inclusion/exclusion criteria below. Coagulopathy will be corrected by ROTEM-guided transfusion protocol (Appendix 2) or conventional, laboratory-based transfusion protocol (Appendix 3) prior to procedure using a 1:1 randomization.

For the primary aim, a total sample size of 202 patients (101 patients in both the non-ROTEM and ROTEM groups) is required to achieve 80% power for a two-sample t-test to detect a 100% increase in the geometric mean of the non-ROTEM group over the ROTEM group. Significance is defined as a two-sided p-value of less than 0.05. This calculation was based off of pilot data which contained 8 ROTEM and 8 non-ROTEM patients. The secondary aim, demonstrating that the proportion of bleeding events in ROTEM patients is equivalent to or less than the proportion in non-ROTEM patients requires a sample size of 446 patients per group. This calculation assumed that both ROTEM and non-ROTEM patients experience a bleeding event 10% of the time. It was further assumed that the proportion of bleeding events in the ROTEM group will be considered to be equivalent to that of the non-ROTEM group if the proportion is no more than 5% larger. The secondary aim is exploratory in nature for the purposes of this protocol as the sample size for the current study is only 202 patients.

No changes in procedural or anesthesia technique will be made for the purposes of the study. All transfusion protocols are currently in use and have been approved by the Ohio State University Wexner Medical Center. Cutoff values and transfusion guides in this protocol have been designed for patients with cirrhosis undergoing liver transplantation based on the currently available evidence in liver transplantation. There are no globally accepted clinical practice guidelines for blood product transfusion in patients with chronic liver disease who undergo invasive procedures. For the purposes of this study, we are incorporating the conventional transfusion protocol utilized by the endoscopy unit, providing a standardized approach to pre-procedure transfusion/s. For the purposes of this study, peri- and post-procedure bleeding events were estimated to occur 10% of the time. This was extrapolated from a study evaluating patients with coagulopathy undergoing bronchoscopy where bleeding rates occurred in 7-11% of procedures. [1] No standard, reported bleeding event rate exists for patients with cirrhosis undergoing endoscopy.

Inclusion criteria

1. Patients of any gender aged 18 years or older

WEXNER MEDICAL CENTER

- 2. Patients who have clinically-documented cirrhosis
- 3. Patients are coagulopathic (INR > 1.5 and/or platelets < 50,000 K/uL)
- 4. Patients are undergoing an endoscopic procedure (esophagogastroduodenoscopy, colonoscopy, flexible sigmoidoscopy, endoscopic retrograde cholangiopancreatography, endoscopic ultrasound), or neurosurgical procedure (placement of an external ventricular drain or placement of an intracranial pressure monitor, or any neurosurgical cranial or spinal procedure that occurs in the operating room during the patient's admission [e.g. craniotomy for evacuation of hematoma or a spinal fusion procedure to address spinal instability])

Exclusion criteria

- 1. Patients must not be pregnant or < 18 years of age
- 2. Patients must not be taking any anticoagulant or antiplatelet medications, except for Aspirin 81 mg daily
- 3. Patients must not have an active infection (per PI discretion)
- 4. Patients must not have any known hemostatic disorder

E. Measurement/Instrumentation

The requested data fields include demographic data, clinicopathologic data, and procedure/operative reports. Please see Appendix 1 for all variables that will be extracted from charts. Any PHI that is collected as part of this prospective study will be maintained in the secure database.

Standard coagulation tests

Conventional coagulation tests (hemoglobin, platelet count, fibrinogen concentration, INR, aPTT, and PT) will be performed in both groups (ROTEM vs. conventional therapy) at two fixed time points (enrollment and within 3 hours after transfusion [which is also within 12 hours of procedure]) in order to compare both groups reliably. Transfusion of blood products (if indicated per the transfusion protocols) will occur within 24 hours of enrollment in both groups. In the post-procedure setting, tests will be performed if any bleeding occurs per the treating physician's discretion.

ROTEM

ROTEM will be performed according to the manufacturer's instruction, using equipment provided by Tem International GmbH. All tests will be performed at the bedside by a clinical perfusionist or study staff member trained to perform ROTEM. The point of care treatment will be guided with the Spine Surgery Algorithm based on the EXTEM, INTEM, FIBTEM and HEPTEM assays. ROTEM will be performed in both groups (ROTEM vs. conventional therapy) at two fixed time points (enrollment and within 3 hours after transfusion [which is also within 12 hours of procedure]) in order to compare both groups reliably.

The Ohio State University

WEXNER MEDICAL CENTER

F. Data Analysis

We will analyze blood product usage, peri- and post-procedure bleeding events, and hospital length of stay comparing ROTEM-guided transfusion protocol versus conventional, laboratory-based transfusion protocol. We will calculate any significant differences between these two cohorts using standard T-Test and multivariate analysis (ANOVA) with support from our Internal Medicine biostatistician.

All study patients will be continuously monitored by the study PI and sub-I's on the inpatient hepatology services. Safety monitoring will be performed on an ongoing basis throughout the entirety of the study. Based on our retrospective study using ROTEM in liver transplantation, we expect FFP transfusion rate to decrease by 50% and cryoprecipitate transfusion rate to increase in the ROTEM group with an overall decrease in blood product use. We expect bleeding rates to be similar in both groups.

IV. References

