Fibrinogen Pre transfusion	Fibrinogen (number)		
Fibrinogen Post transfusion	Fibrinogen (number)		
International Normalized Ratio (INR) Pre transfusion	International Normalized Ratio (INR) (number)		
International Normalized Ratio (INR) Post transfusion	International Normalized Ratio (INR) (number)		
Procedure performed	esophagogastroduodenoscopy = 1, colonoscopy = 2, neurosurgical procedures = 3, other endoscopy procedures = please type out procedure (e.g. endoscopic ultrasound)		
Blood product use prior to procedure	Number of Units		
Type of blood product given prior to procedure	Fresh Frozen Plasma (FFP) = 1, platelets = 2, cryoprecipitate = 3		
Packed Red Blood Cells (pRBC) use post-procedure	Number of units		
Total blood product use post-procedure	Number of units		
Significant blood loss peri-procedure	No = 0, Yes = 1		
Bleeding event 24 hours post-procedure	No = 0, Yes = 1		
Hospital Length of Stay	Number of Days		
Cost	Total cost of ROTEM reagents and supplies used and		
	lab tests (number)		

Division of Gastroenterolgoy, Hepatology & Nutrition Confidential

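### The hypothesis concerns overall blood product use, but the primary endpoint stops at the procedure, units given during it have no data field, and later units are in no stated objective

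*Protocol*

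**What the plan says.** The hypothesis (Protocol III.B) is that the ROTEM-guided protocol "will significantly decrease blood product usage without any increase in procedural bleeding complications". It sets no time window. Section III.F likewise expects total product use to fall in the ROTEM arm, with less FFP and more cryoprecipitate.

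The primary objective (III.C) is limited to the period before the procedure: "To compare the total amount of pre-procedure blood products transfused between the ROTEM-guided transfusion protocol and conventional, laboratory-based transfusion protocol". The secondary objectives are bleeding events, length of stay and hospitalization costs. None compares units given during or after the procedure.

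Section III.E refers to Appendix 1 for all variables to be extracted. On transfusion, Appendix 1 lists:

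- "Blood product use prior to procedure", in units, with product type coded "Fresh Frozen Plasma (FFP) = 1, platelets = 2, cryoprecipitate = 3";
- "Packed Red Blood Cells (pRBC) use post-procedure", in units;
- "Total blood product use post-procedure", in units.

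For the procedure itself it has only a yes/no item on significant blood loss. The schedule in Appendix 4 likewise shows only a bleeding assessment at that time. Eligible procedures (III.D) include cranial and spinal operations in the operating room.

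**The concern.** The endpoint answers a narrower question than the hypothesis asks. A pre-procedure count shows whether fewer units were given before the procedure. It does not show whether those units were avoided or only given later. If some were deferred, the primary result would still read as a saving.

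The two later periods differ. Post-procedure units are collected, so a shift to that period leaves a trace, but no objective uses the data and the field has no end time. Intra-procedure units are not in the list of variables, so a shift to that period leaves none. The gap matters most for operations such as craniotomy and spinal fusion. The Background section also describes algorithm-guided product use during endoscopy as well as before it.

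At stake is the main claim: an overall saving could be reported on evidence that covers only one of three periods.

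**Working it through.** **1. Coverage by period**

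| Period | Units recorded (Appendix 1) | Products identifiable | Compared in a stated objective |
|---|---|---|---|
| Before | Yes | FFP, platelets, cryoprecipitate; no pRBC code | Yes, primary |
| During | No | None | No |
| After | Yes, no time window | pRBC, and a total of all products | No |

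The before and after fields cannot simply be added. The pre-procedure type codes omit red cells, while the post-procedure total may include them.

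**2. Other items that might fill the gap**

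- Major bleeding (III.C) counts a transfusion of at least 2 units of pRBC in the 24 hours after the procedure. Deferred FFP, platelets or cryoprecipitate do not count. Section III.D calls the bleeding aim exploratory: it would need 446 patients per group, and the trial plans 101.
- The cost field in Appendix 1 covers ROTEM supplies and laboratory tests, not blood products.
- The SAP sums pRBC, FFP, platelets, cryoprecipitate and Cell Saver, but for use during OLT, and it names intra-operative blood loss as the primary outcome. OLT is not an eligible procedure in the protocol, so this total does not fill the gap.

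**3. The plan's own figure**

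Section III.D gives 101 per group, 80% power, two-sided 0.05, and a geometric mean ratio of 2.0, which is a log difference of ln 2 = 0.693. The log-scale SD is not stated, so 202 cannot be reproduced independently. Solving for the SD instead:

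SD = 0.693 / [(1.960 + 0.842) × √(2/101)] ≈ 1.76 by the normal approximation, or 1.75 with the t distribution.

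The figure is attainable but cannot be verified. It does not decide this point.

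**4. Size of the gap if units were deferred (shares assumed)**

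Set pre-procedure control use at 100 units and ROTEM use at 50. Let s be the share of the 50 withheld units that is given later, with later use otherwise equal between arms.

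True saving = 50% × (1 − s)

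- s = 25%: 50% × 0.75 = 37.5%
- s = 50%: 50% × 0.50 = 25%
- s = 100%: 50% × 0 = 0%

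The primary endpoint shows 50% in each case.

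**5. Chance of a significant pre-procedure difference with no true saving (assumed)**

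Suppose total use is equal in both arms, the log SD is 1.75, and every ROTEM patient has the same fraction f of product deferred. The pre-procedure ratio is then 1/(1 − f). The t-test on 200 degrees of freedom has noncentrality ln[1/(1 − f)] / [1.75 × √(2/101)].

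| f | Ratio | Chance of p < 0.05 |
|---|---|---|
| 10% | 1.11 | 7% |
| 20% | 1.25 | 15% |
| 30% | 1.43 | 30% |
| 40% | 1.67 | 54% |
| 50% | 2.00 | 80% |

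Deferring half reproduces the ratio the trial is powered to detect, with nothing saved. No corrected sample size follows, because the documents give no mean or SD for total use.

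**The case against.** **The endpoint fits the intervention.** The randomized protocols act before the procedure, and ROTEM is scheduled only at enrollment and before it. Counting units where the intervention acts is legitimate. This stands, and is the reason to keep the primary endpoint. It does not make a pre-procedure count sufficient for a claim about overall use.

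**Deferral is speculative.** On the protocol's own rationale, plasma given to correct an INR is often unnecessary, so plasma withheld would be avoided rather than postponed. This stands as far as it goes: nothing in the documents shows deferral. Nothing in the listed data would rule it out during the procedure either.

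**The trial could see a shift.** A reader might infer that no shift is detectable. The documents do not support that, because total and pRBC units after the procedure are recorded. Only intra-procedure use is missing. Operative reports are among the requested data (III.E), but the same section refers to Appendix 1 for what will be extracted.

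**The direction is not fixed.** A reader might also infer that the ROTEM arm must score lower by construction. That cannot be shown. The transfusion thresholds in Appendices 2 and 3 were not readable in the text available, and the protocol expects cryoprecipitate use to rise.

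**The title is weak evidence.** In "Comparing Blood Product Use and Bleeding Events During and After Endoscopic or Neurosurgical Procedures in Patients with Cirrhosis and Coagulopathy", the words on timing may apply only to bleeding events. The hypothesis is the better support for the mismatch.

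**The figures rest on assumptions.** The shares are not from the documents, and the powered halving is a ratio of geometric means, which is not the same as a fall in total units when counts are skewed. Both points stand, so the figures serve only as illustration.

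**Conclusion.** The point holds as a mismatch of scope and a gap in data capture. The hypothesis and expected result concern use overall, the primary endpoint covers one period, the period of the procedure is not recorded, and the period after it is recorded but not assigned to any objective or time window. It is a risk of bias, not a demonstrated one. If deferral occurred, an apparent 50% saving could correspond to a true saving of 37.5%, 25% or 0% at assumed deferral shares of 25%, 50% or 100%, given equal later use otherwise. How much the missing intra-procedure field matters depends on the share of neurosurgical patients, which the documents do not give. The change is worth making because it is cheap and stops an overall conclusion from resting on a partial count.

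**What to change.** - Keep pre-procedure units as the primary endpoint.
- Add a field to Appendix 1 for units given during the procedure, by product.
- Record the same product set (FFP, platelets, cryoprecipitate, pRBC) before, during and after the procedure, so that the periods can be added.
- Give the post-procedure total a fixed window, such as the 24 hours already used for bleeding. Keep any later units as recorded, so that use beyond the window is not lost.
- Pre-specify total units from enrollment to the end of that window as a secondary endpoint, using the same test as the primary. The protocol names a t-test and the SAP Wilcoxon rank-sum tests, so the two must first be reconciled on the test, as well as on the procedures and the primary outcome.
- Word the conclusion as pre-procedure use unless the total points the same way.

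The cost is one chart field, with red cells added to the pre-procedure codes, and one more secondary endpoint. Data already come from the electronic medical record.

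### The 24-hour major bleeding definition counts only blood volume, so a neurosurgical bleed into a closed space does not meet it unless a hemoglobin fall or red-cell transfusion accompanies it

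*Protocol*

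**What the plan says.** The hypothesis (Protocol III.B) has a safety half. It expects ROTEM guidance to reduce product use "without any increase in procedural bleeding complications versus the conventional, laboratory-based transfusion protocol in patients with cirrhosis undergoing endoscopy and neurosurgical procedures".

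The neurosurgical procedures (Protocol III.C, and III.D inclusion criterion 4) include "placement of an external ventricular drain or placement of an intracranial pressure monitor" at the bedside. In the operating room they include any cranial or spinal procedure, for example "craniotomy for evacuation of hematoma or a spinal fusion procedure to address spinal instability".

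Secondary objective 1 (Protocol III.C) gives two bleeding items for all procedures:

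- The first rests on the operator's own record: "Clinically significant peri-procedure blood loss as documented by the endoscopist or surgeon performing the procedure".
- The second covers the following day and can be met in either of two ways. One is a hemoglobin fall: "Major bleeding during the 24 hours post-procedure, defined as a decrease in hemoglobin of ≥ 2 g/dL". The other is a need for at least 2 red-cell units.

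Appendix 1, which Protocol III.E presents as the full list of chart variables, holds one yes/no field for each item. The second is labelled "Bleeding event 24 hours post-procedure". It has no field for bleeding site, imaging findings or return to the operating room. Appendix 4 schedules an assessment for bleeding without defining it. On laboratory tests, Protocol III.E says: "In the post-procedure setting, tests will be performed if any bleeding occurs per the treating physician's discretion". The SAP describes blood loss in liver transplantation and adds no bleeding-event definition.

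**The concern.** A hemoglobin fall and a red-cell count are reasonable measures where harm comes from the amount of blood lost. In the brain or spinal canal, harm comes mainly from where the blood collects, and a small volume can be serious. That is clinical reasoning, not protocol text, but it fits the procedures the protocol lists. One of these is evacuation of a hematoma, yet re-accumulation of that hematoma would not by itself be an event.

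Missed events pull the comparison towards no difference, which is the result the hypothesis hopes for on safety. The trial could report no increase in bleeding while bleeds after neurosurgery went uncounted.

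**Working it through.** **1. The plan's own figure.** Protocol III.D gives 446 per group for the bleeding comparison: 10% in both arms, margin 5 points. With unpooled variance, 80% power and one-sided 0.05:

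n = 2 × 0.10 × 0.90 × (1.645 + 0.842)² / 0.05² ≈ 445.2, rounded up to 446.

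The figure reproduces. The power and the one-sided level are assumptions here, because III.D states 80% power only for the primary aim and gives a two-sided 0.05. With 101 per group, power for the same margin is about 32% (22% at one-sided 0.025). None of this depends on how a bleed is defined, so it bears on the weight of the comparison and not on the definition.

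**2. Blood loss needed to meet the hemoglobin criterion.** Assumptions, not in the documents: hemoglobin falls in proportion to volume lost; starting hemoglobin 10 g/dL; blood volume 4 to 6 L.

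Loss = (2 / 10) × blood volume = 0.8 L at 4 L, 1.0 L at 5 L, 1.2 L at 6 L.

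**3. Fall caused by an isolated closed-space bleed.** Assumed bleed 30 to 100 mL, blood volume 5 L:

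- 30 / 5000 × 10 = 0.06 g/dL
- 100 / 5000 × 10 = 0.2 g/dL

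That is 3% to 10% of the threshold. With wider assumptions (4 to 5.5 L, hemoglobin 8 to 12 g/dL, bleed 20 to 150 mL):

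- Loss needed for a 2 g/dL fall: (2/12) × 4 = 0.67 L up to (2/8) × 5.5 = 1.4 L.
- Fall caused by the bleed: 20/5500 × 8 = 0.03 up to 150/4000 × 12 = 0.45 g/dL.

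Even the largest of these is under a quarter of the threshold.

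**4. Does the other item cover it?** The operator-documented item is worded as blood loss, with no threshold, no site and no stated end to its window. It could catch a bleed seen during the procedure. It does not reliably reach one found hours later.

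**5. Baseline for the fall.** The definition names none. Appendix 1 has only a pre-procedure and a post-procedure hemoglobin. If the pre-procedure value is the baseline, ordinary operative loss can meet the criterion (about 1 L in step 2). If it is the first post-operative value, ordinary operative loss does not count. Appendix 4 schedules no post-procedure blood collection, so a fall may also go unmeasured.

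**6. Effect on the comparison.** Let f be the neurosurgical share and m the fraction of neurosurgical bleeds missed, equal in both arms. Neither is in the documents. Take a true excess of 5 points (10% against 15%).

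If the same rates hold in every procedure type, the observed difference is 5 × (1 − f × m):

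| f | m | Observed difference (points) |
|---|---|---|
| 5% | 25% | 4.9 |
| 10% | 50% | 4.75 |
| 25% | 100% | 3.75 |
| 50% | 100% | 2.5 |

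If the whole 5-point excess lies in neurosurgical patients, the observed difference is 5 × (1 − m): 2.5 at m = 50%, 0.5 at 90% and 0 at 100%.

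**The case against.** The strongest reply is that the gap is narrower than it looks and its effect on the trial is not shown.

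- **Some of these bleeds will count.** A patient who is re-operated, or who also loses blood at operation, may meet either criterion. A reader might infer that every intracranial or intraspinal bleed is recorded as no event, or that the criterion can never detect one. The documents do not support that: the arithmetic above covers only an isolated bleed under assumed volumes.
- **The field label is loose.** Appendix 1 says bleeding event, not major bleeding, so a chart abstractor could code such a bleed as yes. This stands as a possibility, but it would depart from the written definition and be applied unevenly.
- **The peri-procedure window is open.** Having no end time is ambiguity, not proof that later bleeds are excluded. This stands, but the item is still confined to blood loss.
- **The pooled effect may be small.** The first scenario in step 6 shows little distortion when the neurosurgical share is low. Large distortion needs a large share with most events missed, or an excess confined to neurosurgery, and neither is documented.
- **The aim is already labelled exploratory**, with 446 per group needed and 101 planned. This limits what may be concluded, but it does not repair a definition that leaves out the event.
- **Part of the remedy exists.** Appendix 1 already codes neurosurgical procedures separately, and III.E requests operative reports. No section commits to reporting bleeding by procedure type.

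**Conclusion.** The point holds in conditional form. Under the only written definition, a post-procedure intracranial or intraspinal bleed is not major bleeding unless a hemoglobin fall of at least 2 g/dL or at least 2 red-cell units goes with it. An isolated 30 to 100 mL bleed produces about a tenth of the required fall or less, given 5 L blood volume and hemoglobin of 10 g/dL. The conclusion survives the wider ranges tried.

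The opposite error, counting ordinary operative loss as a bleed, arises only if the pre-procedure hemoglobin is the baseline, which the protocol leaves open.

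A reader might go further and infer that the trial's bleeding comparison as a whole is invalid. The documents do not support this, because the neurosurgical share and the fraction missed are unknown. The primary endpoint, product use before the procedure, is untouched. What is unreliable is a statement of no increase in bleeding for neurosurgical patients. It should be corrected, but it does not threaten the main result.

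**What to change.** Make four changes to the endpoint and its data, with no change to patient care:

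1. For neurosurgical patients, add to the 24-hour endpoint a new or enlarged intracranial or intraspinal hemorrhage on clinically ordered imaging, compared with the last pre-procedure imaging where available, or a re-intervention for bleeding.
2. Add the matching yes/no field to Appendix 1.
3. State which hemoglobin is the baseline for the 2 g/dL fall.
4. Report bleeding by procedure type as well as pooled, using the procedure code already collected.

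The cost is protocol wording and one chart-extracted field, with no mandated imaging. The abstractor must also look up earlier imaging, since some patients enter with an existing hematoma.

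There are two downsides. Silent bleeds are still missed, because detection depends on clinically ordered imaging. Ascertainment could also differ by arm, because Protocol III.A states blinding only for the operator. Both should be acknowledged when the result is reported.
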